Exploratory	 To assess the efficacy of ATI-450 to maintain remission in patients previously managed with anti-IL-1 therapy To assess the 	 Proportion of participants in disease remission over time. Disease remission is defined as having a Physician Global Assessment (PGA) score of absent or minimal and a high sensitivity C-reactive protein (hsCRP) and serum amyloid A (SAA) value within the normal range (≤10 mg/L) or within 30 percent of the baseline value. Proportion of participants in clinical remission over time. Clinical remission is defined as having a PGA score of absent or minimal. Time to relapse; where relapse is defined as a two-point worsening on the PGA scale. Proportion of participants who experience re-emergence of disease symptoms after discontinuation of ATI-450. Re-emergence is defined as a daily Key Symptom Score (KSS) ≥ 3 points higher than baseline for at least 2 consecutive days. KSS is derived from the patient-administered daily health assessment form (DHAF). Proportion of participants with a mean KSS no more than 2 points higher than baseline for at least 6 out of 8 weeks during the treatment period. Change from baseline in PGA. Change from baseline in hsCRP and SAA. Change from baseline in serum
	Pharmacodynamics (PD) of ATI-450 in patients with CAPS To assess the Pharmacokinetics (PK) of ATI-450 in patients with CAPS	 cytokines IL-1β, IL-1α, IL-6, IL-18, and TNF-α ATI-450 concentrations at trough

Study Design:

This is a Phase 2a, open-label, single-arm, study to investigate the safety, tolerability, efficacy, and PD of ATI-450 to maintain remission in patients \geq 18 years old with CAPS previously managed with anti-IL-1 therapy.

Patients with a PGA score of "minimal" or less and a hsCRP and SAA value within the normal range, and are considered to have achieved remission (i.e., those values for PGA, hsCRP, and SAA) as a result of successful anti-IL-1 therapy, will be eligible for study entry.

Patients will be entered into the study at the time of their next scheduled dose of anti-IL-1 therapy. Rather than receiving anti-IL-1 therapy, ATI-450 will be dosed at 50 mg twice daily (BID) orally for 12 weeks. Patients will be assessed for safety and disease activity at 2 weeks, 4 weeks, 8 weeks, and 12 weeks.

At the end of 12-weeks, Day 84 (+/- 1 day), patients will stop ATI-450 and conduct end of study assessments.

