Patients will complete safety follow-up visits on site 7 Days (+4 days) after the last dose of ATI-450 and via a phone call 30 Days (+/-3 days) after the last dose.

Patients should not start their anti-IL-1 therapy until all safety follow-up Day 7 assessments have been completed. However, in the event of a safety concern, patients will be allowed to return early or restart their anti-IL-1 therapy prior to completing the safety follow-up Day 7 visit at the discretion of the investigator.

The study will consist of up to an 8-week screening period, a 12-week treatment period, and a 4-week safety follow-up period. The total duration of the study for patients remaining until their final follow-up assessment will be up to 24 weeks.

Up to 10 patients whose eligibility is confirmed at baseline will be enrolled in the study.

Study Duration:

The start of the study will be the date on which the first patient provides informed consent, and the end of the study will be the date of the last patient's last assessment. It is anticipated that total duration could be up to 24 weeks.

Planned Number of Patients: It is planned to enroll up to 10 patients.

Target Population:

Inclusion Criteria

Patients must meet the following criteria to be eligible for participation in the study:

- 1. Diagnosis of Familial Cold Autoinflammatory Syndrome, Muckle-Wells Syndrome, or Neonatal Onset Multisystem Inflammatory Disease. Prior agreement between the Investigator and Aclaris for study eligibility is required for patients who do not have a molecular diagnosis of NALP3 mutations available (either testing not performed, or testing performed, but negative) upon study entry. For those patients who have not been molecularly tested for NALP3 mutations, molecular testing should be performed during the study.
- 2. Patients with a PGA score of "minimal" or less and who are considered to have achieved that response as a result of successful anti-IL-1 therapy.
- 3. Continuous Treatment with anti-IL-1 therapy for at least 6 months.
- 4. Able to understand and comply with study procedures and able to provide informed consent.
- 5. Male or non-pregnant, non-nursing female patients at least 18 years of age, inclusive.
 - Female patients who are of childbearing potential must use 2 methods of highly effective contraception* one of which must be a physical barrier- for the duration of the study and for 30 days after the last dose.

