 - Any other finding that is considered clinically significant
- 17. A confirmed diagnosis of Covid-19 at baseline or at any time during the study.

Test Product:

Name: ATI-450 Dose: 50 mg BID

Mode of administration: Oral tablets

Control Product:

None

Statistical Methods:

Determination of Sample Size

The sample size for this study was determined based upon feasibility constraints as opposed to a formal power computation. Up to 10 patients are planned to be enrolled.

Analysis Populations.

- The Intent-to-treat (ITT) population will include all patients who have been administered at least one dose of study medication.
- The Per-Protocol (PP) population will include all patients who complete 12-weeks of treatment and 4-weeks of safety follow-up and have completed study assessments.

Efficacy Analyses

All efficacy summaries will be conducted on both the ITT and PP populations.

- Proportion of participants in disease remission over time; where disease remission is defined as having a PGA score of minimal or better and a hsCRP and SAA value within the normal range or within 30 percent of the baseline value (ITT and PP population).
- Proportion of participants in clinical remission over time; where clinical remission is defined as having a PGA score of minimal or better (ITT and PP population).
- Proportion of participants who experience an increase over baseline in daily KSS of ≥ 3 for at least two days after discontinuation of ATI-450 over time (PP population).
- Proportion of participants who maintain a mean KSS of no more than 2 points higher than baseline in at least 6 out of 8 weeks in the ITT and PP population.
- Change from baseline in PGA and KSS scores will be reported descriptively over time (ITT and PP population).
- Change from baseline in hsCRP and SAA and percent change from baseline in hsCRP and SAA will be summarized over time using continuous statistical summary measures.

 Determination of sustained treatment effect for hsCRP and SAA will be based upon the median percent change from baseline in the ITT and PP population.

Safety Analyses

The ITT population will be used for the analysis of safety data (AEs, exposure to study medication, clinical laboratory values, vital signs, and ECG).

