2 STUDY OBJECTIVES AND ENDPOINTS

The objectives and endpoints for this study are provided in Table 2 below.

Table 2 Study Objectives and Endpoints

Objectives		Endpoints			
Primary	To assess the safety and tolerability of ATI-450 to maintain remission in patients with CAPS previously managed with anti-IL-1 therapy	Number and percent of adverse events (AEs) and serious adverse events (SAEs); mean change from baseline in laboratory values, vital signs, and electrocardiograms (ECGs).			
Secondary	To assess the efficacy of ATI-450 to maintain remission in patients previously managed with anti-IL-1 therapy	 Proportion of participants in disease remission. Disease remission is defined as having a Physician Global Assessment (PGA) score of absent or minimal and a high sensitivity C-reactive protein (hsCRP) and serum amyloid A (SAA) value within the normal range (≤10 mg/L) or within 30 percent of the baseline value. Proportion of participants in clinical remission. Clinical remission is defined as having a PGA score of absent or minimal. Time to relapse; where relapse is defined as a two-point worsening on the PGA scale. Proportion of participants who experience a re-emergence of disease symptoms after discontinuation of ATI-450. Re-emergence is defined as an increase in daily Key Symptom Score (KSS) ≥3 for at least two consecutive days. KSS is derived from the patient-administered daily health assessment form (DHAF). Proportion of participants with a mean KSS no more than 2 points higher than baseline for at least 6 out of 8 weeks during the treatment period. Change from baseline in PGA. Change from baseline in PGA. 			

		Change from baseline in hsCRP and SAA.
Exploratory	 To assess the Pharmacodynamics (PD) of ATI-450 in patients with CAPS To assess the pharmacokinetics (PK) of ATI-450 in patients with CAPS 	 Change from baseline in serum cytokines IL-1β, IL-1α, IL-6, IL-18 and TNF-α ATI-450 concentrations at trough

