3 STUDY PLAN

3.1 Overall Study Design and Plan

The study visit schedule and planned assessments at each visit are detailed in Table 1.

This is a Phase 2a, open-label, single-arm study to investigate the safety, tolerability, efficacy, PK, and PD of ATI-450 to maintain remission in patients with CAPS previously managed with anti-IL-1 therapy. Up to 10 patients are planned to be enrolled in the study. The study will consist of an up to 8-week screening period, a 12-week treatment period, and a 4-week safety follow-up period. The total duration of the study for patients remaining in the study until their final safety follow-up assessment will be up to 24 weeks.

The investigator will obtain signed informed consent from the patient before any study procedures are performed. For further details regarding the informed consent process, see Section 9.3. During the screening visit each patient will be required to have all assessments performed as outlined in the Schedule of Assessments (Table 1).

Patients whose eligibility is confirmed at baseline will begin dosing ATI-450 tablets (50 mg BID). Such patients will be in protocol-defined remission due to prior treatment with an anti-IL-1 biologic. Dosing will begin on the day that the next dose of their anti-IL-1 therapy is scheduled at which time anti-IL-1 therapy will be discontinued.

The first dose of ATI-450 (50 mg BID) will be taken at the following times (based on anti-IL-1 therapy):

- Anakinra: 24 hours (+/- 1 hour) after last administration or at approximate time of regular anakinra dose.
- Canakinumab: 8 weeks (+/- 1 week) after last administration.
- Rilonacept: 1 week (+/- 1 day) after last administration.

ATI-450 will be administered orally for 12-weeks. Patients will attend clinic visits on Days 14, 28, 56, and 84 (+/-1 day) for safety, efficacy, PK and PD assessments. Patients will begin recording disease symptoms in their daily diary card 7 days prior to beginning administration of ATI-450, or immediately starting at the screening visit if the Day 1 visit is scheduled to occur less than 7 days after the screening visit. Patients will continue to complete their diary until completion of the safety follow up Day 7 visit.

At the end of 12-weeks, Day 84 (+/- 1 day), patients will stop ATI-450 and conduct end of study assessments. Patients will complete safety follow-up visits on site 7 Days (+4 days) after the last dose of ATI-450 and via a phone call 30 Days (+/-3 days) after the last dose.

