5.2.1.1 Maintenance of Disease Remission and Clinical Remission

Maintenance of disease remission will be assessed during the treatment period. Disease remission is defined as having a PGA score of absent or minimal and a hsCRP and SAA value within the normal range (≤10 mg/L) or within 30 percent of the baseline value.

Maintenance of clinical remission will be assessed during the treatment period. Clinical remission is defined as having a PGA score of absent or minimal.

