8.4 Statistical Methods

8.4.1 Efficacy Analyses

All efficacy summaries will be conducted on both the ITT and PP populations.

- Proportion of participants in disease remission over time; where disease remission is defined as having a PGA score of minimal or better and a hsCRP and SAA value within the normal range or within 30 percent of the baseline value (ITT and PP population).
- Proportion of participants in clinical remission over time; where clinical remission is defined as having a PGA score of minimal or better (ITT and PP population).
- Time to relapse; where relapse is defined as a two-point worsening on the PGA scale in the ITT population.

- Proportion of participants who experience a daily increase in KSS \geq 3 on at least two consecutive days after discontinuation of ATI-450 over time (PP population).
- Proportion of participants who maintain a mean KSS of no more than 2 higher than baseline for at least 6 out of 8 weeks in the ITT and PP population.
- Change from baseline in PGA and KSS scores will be reported descriptively over time (ITT and PP population).
- Change from baseline in hsCRP and SAA and percent change from baseline in hsCRP and SAA will be summarized over time using continuous statistical summary measures. Determination of sustained treatment effect for hsCRP and SAA will be based upon the median percent change from baseline in the ITT and PP population.

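### Disease remission: the 30 percent marker limit has no direction, so an hsCRP or SAA that falls by more than 30% but stays above 10 mg/L counts as lost remission

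*Combined protocol and SAP*

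**What the plan says.** Disease remission combines a PGA of absent or minimal with a marker condition. Section 5.2.1.1 words that condition as "hsCRP and SAA value within the normal range (≤10 mg/L) or within 30 percent of the baseline value". The same 30 percent wording appears in the synopsis endpoint table, the synopsis efficacy analyses, Table 2 and Section 8.4.1. None of them says whether the 30 percent applies to rises, falls or both.

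Table 2 does state a direction for another endpoint, the symptom score: "mean KSS no more than 2 points higher than baseline for at least 6 out of 8 weeks during the treatment period".

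Baseline is the last non-missing value on or before the date of first dosing (Section 8.1). Section 5.2.3 sets the normal range at 10 mg/L or less for both markers.

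The entry text is not consistent about the markers:

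- The synopsis study design asks for a PGA of minimal "or less and a hsCRP and SAA value within the normal range, and are considered to have achieved remission".
- Inclusion criterion 2, in the synopsis and in Section 4.1, asks for a PGA of minimal "or less and who are considered to have achieved that response as a result of successful anti-IL-1 therapy", and sets no hsCRP or SAA limit.
- Section 3.1 adds: "Such patients will be in protocol-defined remission due to prior treatment with an anti-IL-1 biologic".

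**The concern.** To be within 30 percent of a value ordinarily means no more than 30 percent away from it on either side. Read that way, the rule penalises improvement. A patient with a raised baseline marker that then falls substantially, but not to 10 mg/L, is outside the band and outside the normal range, and so is counted as having lost remission. A patient whose marker rises by up to 30 percent is counted as still in remission. Because the symptom-score rule in the same table is explicitly one-sided, a programmer comparing the two has a textual reason to code the marker rule as two-sided.

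Disease remission is the only endpoint that combines the physician's assessment with both markers. Both markers must pass, so one improved but still raised marker is enough to fail the patient. With at most 10 patients, a single wrong classification is visible in the reported proportion.

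**Working it through.** The plan contains no figure that depends on this rule, so there is nothing to reproduce. The check compares the rule as written with a one-sided version, marker by marker.

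**Inputs.** Cut-off of 10 mg/L and tolerance of 30 percent (Sections 5.2.1.1 and 5.2.3); baseline B as defined in Section 8.1; at most 10 patients (Section 8.3). The values of B below are assumptions for illustration, because the documents give none.

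**Rules, for a post-baseline value v.**

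- As written: pass if v ≤ 10, or 0.7B ≤ v ≤ 1.3B.
- One-sided: pass if v ≤ 10, or v ≤ 1.3B.

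**Where the 30 percent limb matters.**

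- It adds passing values only if 1.3B > 10, so B > 10/1.3 = 7.7 mg/L.
- An improved value fails only if 10 < v < 0.7B. That interval is non-empty only if B > 10/0.7 = 14.3 mg/L.
- Between 7.7 and 14.3 mg/L, the limb widens the pass region and no improvement can fail.

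As a percentage fall, the failing values are falls of more than 30% and less than 100 × (1 − 10/B)%.

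| Assumed B (mg/L) | Improved values that fail | Size of fall | Highest passing value (1.3B) |
|---|---|---|---|
| 15 | between 10 and 10.5 | 30% to 33% | 19.5 |
| 20 | between 10 and 14 | 30% to 50% | 26 |
| 30 | between 10 and 21 | 30% to 67% | 39 |
| 40 | between 10 and 28 | 30% to 75% | 52 |
| 60 | between 10 and 42 | 30% to 83% | 78 |

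At B = 20, a value of 26 passes, 14 passes, 13 and 11 fail, and 10 passes: status goes from pass to fail and back to pass as the marker falls. At B = 30, a rise to 39 passes and a fall to 15 (−50%) fails.

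A grid of baselines from 0.5 to 60 mg/L and values from 0.5 to 80 mg/L confirmed that the two rules disagree only when the value is below baseline and the baseline is above 14.3 mg/L. The one-sided rule therefore never passes a worsened marker that the written rule fails.

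**Can a baseline above 14.3 mg/L occur?** Under inclusion criterion 2, yes, since it has no marker limit. Under the synopsis design text, entry markers should be normal, but screening may be as early as Day −56 (Table 1), and the baseline sample is normally the pre-dose draw at Visit 2. Section 3.1 places that visit when prior treatment is next due: "Dosing will begin on the day that the next dose of their anti-IL-1 therapy is scheduled". The baseline value may therefore be higher than the screening value. If normal markers were enforced on the baseline sample itself, the problem could not arise.

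**Effect per patient.** One misclassified patient changes the proportion at that visit by 1/10 = 10 points, or 1/5 = 20 points if only 5 are enrolled.

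**The case against.** The best reply is that this is an unstated direction rather than a mistaken rule. The section is about maintaining remission, and the neighbouring limb (≤10 mg/L) never penalises a low value, so the 30 percent is naturally read as a tolerance for worsening. Section 8.1 also promises a SAP with more detail. The sponsor probably did intend a one-sided limit. That does not dispose of the point: nothing in the supplied text says so, and the literal wording gives the wrong answer if it is followed.

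The second reply is that the case is narrow. It needs a baseline above 14.3 mg/L, a fall of more than 30%, a value still above 10 mg/L, and a PGA of absent or minimal, in a patient who has just stopped at least six months of successful anti-IL-1 therapy. Eligibility is also reviewed again at baseline (Table 1 and Section 5.1.1). The narrowness stands. The baseline review helps only if the criteria being reviewed include a marker limit, and criterion 2 does not. Nor do the documents say whether the central laboratory's Day 1 result is available before the first dose.

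The third reply is that little depends on it. The endpoint is descriptive, PGA-only remission and percent change in both markers are reported alongside it, and the error can only understate remission. All of that stands, and it limits the severity.

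**Conclusion.** The concern holds. As written, the marker limb is a band from 0.7 to 1.3 times baseline, and any value strictly between 10 mg/L and 0.7 times baseline is scored as loss of remission although the marker improved. This requires a baseline above 14.3 mg/L for that marker. How many patients would be affected cannot be derived from the documents and may be none; each one lowers the visit proportion by 10 points at n = 10.

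The consequence is limited. The primary objective is safety, and disease remission is listed as exploratory in the synopsis and secondary in Table 2. It carries no test or success criterion. The conclusion assumes that the rule is programmed literally and that no later SAP text makes it one-sided. The size of the upper tolerance is the sponsor's choice and is not questioned. This should be fixed, and it is better settled before data are seen, because reinterpreting the rule in an open-label study once results are known would look post hoc.

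**What to change.** In the synopsis endpoint table, the synopsis efficacy analyses, Table 2, Section 5.2.1.1 and Section 8.4.1, replace the marker condition with: *each of hsCRP and SAA is ≤10 mg/L or no more than 30% above its baseline value*. This also makes explicit that each marker is judged against its own baseline and that the two may qualify by different limbs; the sponsor should confirm that this is intended. Optionally, also report the proportion with both markers at or below 10 mg/L.

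The cost is one phrase in five places, with no change to visits, data collection or the upper tolerance.

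Separately, reconcile the marker requirement in the synopsis study design with inclusion criterion 2 in the synopsis and Section 4.1. Which version applies is for the sponsor to decide. Unlike the wording change, that decision could affect who is enrolled.

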5.2.1.2 Time to Relapse

Time to relapse will be assessed during the treatment period. Relapse is defined as a two-point worsening on the PGA scale.

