5.2 Efficacy Assessments

5.2.1 Physician Completed Efficacy Questionnaire

The Physician's Global Assessment of Autoinflammatory Disease Activity (PGA) is a measure to be completed by the investigator or designee. The PGA uses a 5-point rating scale: absent, minimal, mild, moderate, and severe. The investigator will select a rating based on the patient's current disease activity at the time of the visit.

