6.6 Concomitant Medication

The following medications are prohibited during the duration of the study:

- 1. Systemic immunosuppressant or immunomodulatory therapy (excluding anti-IL-1 therapy for treatment of CAPS during screening and follow-up period). See section 3.1 for washout information.
- 2. JAK inhibitors (systemic and topical).
- 3. Systemic corticosteroids (Intranasal, inhaled, and topical ocular corticosteroids) are allowed.

All medication (including vaccines, over-the-counter or prescription medicines, vitamins, and/or herbal supplements) taken from 30 days before start of screening until the end of the follow-up period will be recorded in the appropriate section of the eCRF. The following details must be recorded in the eCRF:

- Medication name (ideally the generic name)
- Reason for use
- Start and end date of administration
- The dose and frequency of administration

The medical monitor should be contacted if there are any questions regarding prior or concomitant medication or procedures.

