8.4.5 Handling of Missing Values

Missing data will not be imputed for the safety summaries or the efficacy summaries conducted on the PP population.

For efficacy summaries conducted on the ITT population a model based multiple imputation procedure will be used to impute missing data, where appropriate. Rules for imputation of missing efficacy data will be detailed in the SAP.

Patients who prematurely discontinue the study will be evaluated based on the data collected at each visit attended. Data collected during the withdrawal visit will be used as an end of study assessment for these patients. If the withdrawal visit was performed >1 day after the last dose was administered, then the previous visit will be used as the end of study assessment.

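### Without a recorded two-point PGA worsening, stopping ATI-450 for CAPS symptoms or returning to anti-IL-1 therapy is not a relapse, and the patient can still be recorded as in remission

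*Combined protocol and SAP*

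**What the plan says.** **Relapse.** Section 5.2.1 states: "The PGA uses a 5-point rating scale: absent, minimal, mild, moderate, and severe". The rating reflects disease activity at the visit. Section 5.2.1.2 places relapse within the treatment period and adds: "Relapse is defined as a two-point worsening on the PGA scale". Section 8.4.1 lists the analysis as "Time to relapse; where relapse is defined as a two-point worsening on the PGA scale in the ITT population". Neither section, nor the synopsis or Table 2, says what happens to time to relapse when a patient stops ATI-450 or switches treatment. There is no event, censoring or competing-event rule.

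**Remission.** Section 5.2.1.1 states: "Clinical remission is defined as having a PGA score of absent or minimal". It also states: "Disease remission is defined as having a PGA score of absent or minimal and a hsCRP and SAA value within the normal range", with a value within 30 percent of baseline accepted as an alternative. Neither definition depends on which treatment the patient is taking.

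**Anti-IL-1 therapy.** Section 6.6 prohibits "Systemic immunosuppressant or immunomodulatory therapy (excluding anti-IL-1 therapy for treatment of CAPS during screening and follow-up period"), so the exemption does not cover the treatment period. Section 3.1 allows an early restart before the follow-up Day 7 visit for a safety concern, and gives that restart no consequence for any endpoint.

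**Early stopping and missing data.** Section 8.4.5 says: "For efficacy summaries conducted on the ITT population a model based multiple imputation procedure will be used to impute missing data, where appropriate". It continues: "Rules for imputation of missing efficacy data will be detailed in the SAP". No separate SAP text is among the documents. For patients who leave early, the withdrawal visit serves as the end-of-study assessment. If it took place more than 1 day after the last dose, the previous visit is used instead. Section 4.4.1 asks that early discontinuers complete the end-of-study assessments. Its list of reasons for stopping contains no item for flare or lack of effect.

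**The concern.** The efficacy question is whether ATI-450 can take the place of anti-IL-1 therapy. A patient who has to go back to that therapy, or who stops ATI-450 because CAPS symptoms have returned, has answered it in the negative. The written definition of relapse does not see that outcome unless the PGA has also moved two points at a visit.

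The situation is foreseeable. Section 3.2 says many patients do very well on existing therapy and that time off it should be kept short because prolonged relapse can do harm. A worsening patient therefore has a reason to stop and an effective treatment to return to.

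The other efficacy analyses do not reliably fill the gap. The per-protocol population in section 8.2 contains completers only. Symptom re-emergence in section 5.2.2.1 is assessed after the treatment period has been completed. Section 4.4.1 lets the sponsor replace patients who stop early. The error runs in favour of ATI-450, and a single-arm study has no control group in which the same error would appear.

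**Working it through.** The plan gives no figure to reproduce: section 8.3 sets up to 10 patients by feasibility, without a power calculation. The check is to read the definitions against each other and then do illustrative arithmetic.

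**Step 1. PGA moves from the two eligible baselines.** Inclusion criterion 2 requires *minimal* or less. Code absent = 0, minimal = 1, mild = 2, moderate = 3, severe = 4 (my coding). Relapse means a rise of at least 2; clinical remission means a score of at most 1.

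| Baseline | Visit | Clinical remission | Relapse |
|---|---|---|---|
| absent (0) | mild (2) | no | yes (2 − 0 = 2) |
| minimal (1) | mild (2) | no | **no** (2 − 1 = 1) |
| minimal (1) | moderate (3) | no | yes (3 − 1 = 2) |

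A patient who enters at *minimal*, reaches *mild*, stops and returns to anti-IL-1 therapy has lost remission at that visit but has no relapse.

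**Step 2. A flare between visits.** Treatment visits are at Days 14, 28, 56 and 84, so the last two intervals are 56 − 28 = 28 and 84 − 56 = 28 days. Take a patient in remission at Day 28 who flares and stops at about Day 40 and is seen two days later. Two days is more than 1 day, so section 8.4.5 makes Day 28, in remission, the end-of-study value. If the late visit shows a two-point worsening, the text does not say whether it still counts as a relapse.

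**Step 3. A failure that is captured.** Take a patient who is *mild* at Day 28 and then stops. A withdrawal visit within 1 day of the last dose gives the current PGA. A later one is replaced by Day 28, which is *mild*. If the PGA is still *mild* at a timely visit, the end-of-study value is not in remission either way.

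**Step 4. Size.** Assumptions, none of them in the documents:
- N = 10.
- f patients stop for symptoms or return to anti-IL-1 therapy without a recorded two-point worsening.
- There are no other relapses.
- A share p of the other N − f patients is in remission, with p = 1.0 or 0.8.

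Formulas:
- Relapse-free as written: 100%, because there are no events. With the f patients counted: (N − f)/N.
- Remission if the f patients are imputed at the continuers' share: p.
- Remission if the previous visit, in remission, is used for them: [(N − f)p + f]/N.
- Remission with the f patients counted as failures: (N − f)p/N.

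| f | Relapse-free, as written / counted | Remission, p = 1.0: imputed / previous visit / counted | Remission, p = 0.8: imputed / previous visit / counted |
|---|---|---|---|
| 1 | 100% / 90% | 100% / 100% / 90% | 80% / 82% / 72% |
| 3 | 100% / 70% | 100% / 100% / 70% | 80% / 86% / 56% |
| 5 | 100% / 50% | 100% / 100% / 50% | 80% / 90% / 40% |

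Per patient, the relapse-free share shifts by 1/N = 10 points. Remission shifts by p/N = 8 to 10 points under that imputation, and by 1/N = 10 points under the previous-visit rule.

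**The case against.** The strongest objection concerns remission. A reader might infer that patients who become *mild*, stop and switch would be imputed as in remission, giving a figure near 100%. The documents do not support that. Suppose 4 of 10 patients are *mild* at Day 28 and stop then, and 6 stay in remission. By step 3 the four have an end-of-study value of *mild*, so end-of-study remission is 6/10 = 60%. At most their Day 56 value would be imputed. The form of the imputation model is not given either. Section 8.4.5 says only that it is model based and applied where appropriate, and a model that uses each patient's own *mild* value need not return remission. The rules are left to the SAP. This objection stands and limits the remission part.

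A reader might also infer that nothing sets aside values taken after rescue. The more-than-1-day rule does set aside late withdrawal visits. The difficulty is what it puts in their place.

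Other objections stand in part:
- Loss of clinical remission is an endpoint of its own, so a *mild* rating at an attended visit is reported. That does not help time to relapse or a flare between visits.
- That a worsening patient will stop and switch is a prediction, and the number who would do so is unknown.
- A composite endpoint is one legitimate choice among several. On-treatment and competing-event approaches exist, but the plan states none.
- The stakes are limited. Safety is primary, the efficacy summaries are descriptive, and efficacy is exploratory in the synopsis and secondary in Table 2. With 10 patients precision is poor anyway: exact 95% intervals are 69% to 100% for 10/10 and 35% to 93% for 7/10. Imprecision does not excuse an error that always points the same way.

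**Conclusion.** The point holds for time to relapse and, more narrowly, for remission. The relapse definition is a stated rule, and under it a failure without a recorded two-point PGA worsening is not an event. With N = 10 and no other relapses, each such patient overstates the relapse-free share by 10 percentage points; three of them make it 100% instead of 70%.

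For remission the overstatement is at most about 10 points per patient. It arises only when the last usable visit still showed remission or when later visits are imputed as remission. A withdrawal visit within 1 day of the last dose captures the failure. The stronger conclusion, that failures are generally turned into remissions, is not supported. A SAP could still settle the imputation part, but the protocol itself fixes the relapse definition and the previous-visit rule.

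The sizes rest on assumed numbers of failures and assumed remission shares. The change should be made before database lock. Because the affected endpoints are descriptive and not primary, it is a recommendation and not a condition for running the study.

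**What to change.** Change sections 5.2.1.2, 8.4.1 and 8.4.5, and carry the change into the SAP. This is an endpoint rule only and leaves rescue and stopping as they are.

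1. Count as relapse, on its date, the earliest of: (a) a two-point PGA worsening; (b) a first dose of anti-IL-1 therapy, another prohibited immunosuppressant or a systemic corticosteroid, given for CAPS before the end of the planned treatment period; (c) stopping ATI-450 for CAPS symptoms or lack of effect.
2. Score these patients as not in disease or clinical remission at every later scheduled treatment visit. This overrides both the previous-visit rule and imputation.
3. Keep multiple imputation for missing data unrelated to CAPS activity.
4. Show the PGA-only time to relapse as a supporting result.
5. Add CAPS symptoms or lack of effect to the eCRF as a recorded reason for stopping.

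The cost is wording plus one eCRF field. Stop dates (section 6.8) and the dates and reasons for concomitant medication (section 6.6) are already recorded; the stop reason is not shown to be. The efficacy figures may come out less favourable.
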